## 15.2 Extent of Exposure

Investigational product exposure will be summarized for each treatment using the total number of doses taken, total dose received, the duration of treatment, and the number and percentage of subjects who had a dose interruption. Duration of treatment is defined as the last dose date minus the first dose date plus 1.

The total dose received formulated in hydroxypropyl methylcellulose (HPMC) capsules will be provided in bottles containing 65 capsules of 50 mg dose or 150 mg dose (based on freebase

CT1812 fumarate salt) or its matching placebo. Subjects are expected to take 2 capsules per day. Total dose received will be calculated by (50 mg or 150 mg) × actual number of used capsules in total.

Investigational product compliance will be calculated as follows:

- Compliance (%): (actual number of capsules taken in total) / (number of prescribed capsules to be taken) × 100
- Actual number of capsules taken in total: Sum of Number of Capsules Taken
- Number of prescribed capsules to be taken: duration of study drug administration (days) × 2 capsules per day
- Duration of study drug administration (days) = date of last administration – date of first administration + 1

Investigational product compliance will be presented as descriptive statistics, also will be summarized by treatment group using counts and percentages as categorized below:

- >100%
- >90% to 100%
- >80% to 90%
- ≤80%

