Serial monitoring of ALT/AST/bilirubin and INR will be performed, initially with repeat values within 4 days of discontinuation of study drug. If LFTs are still elevated 4 days post-study drug interruption, participants should have LFTs checked again 4 days later (+/- 1 day). The site investigator and medical monitor should agree to a plan for further LFT monitoring depending on whether the LFTs are still increasing or trending towards normal. Repeat testing should be carried out until LFTs have normalized. The LFTs in this instance can also be run locally for more rapid turnaround.

In the event a reversible etiology is found to explain the elevated liver enzymes (such as a common bile duct stone), drug may be restarted following normalization of LFTs, and after discussion between the Medical Monitor and site PI.

Study drug will be temporarily discontinued if a participant does not achieve the aforementioned levels of elevated LFTs but has an elevation of ALT or AST $>3 \times$ ULN. These participants will have LFTs retested within 4 days after their last dose of study drug. If LFTs are still elevated 4 days post-study drug interruption, participants will have LFTs checked again 4 days later (± 1 day), and the site PI and medical monitor will agree to a plan for further monitoring of the findings. The LFTs in this instance can also be run locally for more rapid turnaround.

LFTs do not need to be intensively monitored when ALT and AST are $\leq 3 \times$ ULN with no elevation of bilirubin, however the investigator and the medical monitor will formulate a plan for serial testing of LFTs. Cessation of dosing is not required in this circumstance but may be temporarily interrupted at the discretion of the investigator.

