7.2 Duration of Study

Screening procedures will occur on Days -42 to -1. Eligible subjects will return to the clinic at Baseline/Day 1 visit for randomization into the trial. Daily dosing will continue through Day 182. The maximum total duration of subject participation in the study is up to 254 days including screening.

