9.3.1 Concomitant COVID-19 Treatment Restrictions

- If a subject is treated for COVID-19 infection, the following recommendations would allow the subject to remain in the trial.
 - If the subject is prescribed Paxlovid™, CT1812 dosing should be held coinciding with the day Paxlovid™ is first administered. CT1812 should not be administered for the 5-day course of Paxlovid™, in addition to 7 additional days (12 days total holding of CT1812) to allow for regeneration of the 3A4 isoenzyme. Normal dosing of CT1812 can then resume.

- If a subject is prescribed Lagevrio™ (molnupiravir), the preclinical data indicates it is neither metabolized by CYP isoenzymes, nor does it interact with them. Therefore, no cessation of CT1812 is required if Lagevrio™ is employed.

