## 8. ANALYSIS POPULATIONS

The populations for analysis will include the enrolled population, intent-to-treat (ITT) population, safety population, completers/compliers population, pharmacokinetic (PK) population, pharmacodynamics (PD) population, and the skin biopsy population.

- The enrolled population will include all subjects that signed the Informed Consent Form (ICF). Subject disposition summaries and data listings will be based on this population.
- The safety population will include all subjects in the ITT population who received at least one dose of study drug. Subjects in this population will be analyzed according to the treatment they received, regardless of which treatment they were randomly assigned. All safety and tolerability analyses will be based on this population and treatment assignment.
- The ITT population will include all subjects that were randomly assigned to study drug. Subjects in this population will be analyzed according to the treatment to which they were randomized, regardless of what treatment they received. All efficacy analyses will be based on this population and treatment assignment.
- The completers /compliers population will include all randomized subjects who completed the study (i.e., who did not prematurely withdraw) and had between 80%-120% compliance with study drug over the course of the study. There is no expectation that a subject included in the completers/compliers population will have attended every single scheduled visit; as long as the subject completed the study and met the study drug compliance criteria, they will be included in the population. Subjects in this population will be analyzed according to the treatment to which they were randomized, regardless of what treatment they received. This population will be used for sensitivity analyses of the efficacy endpoints.

The following subject populations will be used for PK/PD analyses:

- The PK population will include all subjects in the safety population who had at least 1 quantifiable concentration of CT1812.
- The PD population will include all subjects in the safety population who had an exploratory biomarker evaluation.

The following subject population will be used for the summarization of skin biopsy results:

- The skin biopsy population will include all subjects in the safety population with Syn-One Test skin biopsy results available.

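### The compliance figure that gates the completers/compliers set runs only to the last dose taken and counts ordered hold days as missed, so it does not measure compliance over the planned 182 days

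*SAP*

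**What the plan says.** **The gate.** SAP 8 admits to the completers/compliers set randomized subjects "who completed the study (i.e., who did not prematurely withdraw") and who "had between 80%-120% compliance with study drug over the course of the study". On its use it says: "This population will be used for sensitivity analyses of the efficacy endpoints". SAP 10 applies it to all efficacy endpoints.

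**The figure behind the gate.** SAP 15.2 defines compliance as capsules taken over capsules prescribed. The prescribed count starts from "Number of prescribed capsules to be taken: duration of study drug administration (days"), times two capsules a day, and the duration is "date of last administration – date of first administration + 1". Neither the planned treatment length nor interruptions appear in the formula.

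**The planned course.** Protocol 7.2: "Daily dosing will continue through Day 182".

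**Holds that the protocol itself orders.** Protocol 6.3.1: "Study drug will be temporarily discontinued if a participant does not achieve the aforementioned levels of elevated LFTs" but ALT or AST exceeds three times the upper limit of normal. No maximum length is stated. Protocol 9.3.1 orders a pause of fixed length with Paxlovid: "12 days total holding of CT1812".

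**The concern.** SAP 8 asks for compliance across the whole study, but the only compliance formula in the SAP covers the span from first to last dose taken. This has two consequences.

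- If a subject stops and does not restart, the untreated remainder drops out of the denominator. The percentage then describes only the time on drug.
- If a subject is held on the protocol's instruction and restarts, the held days sit inside the first-to-last-dose span and count as prescribed but not taken.

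Membership can therefore turn on whether dosing resumed rather than on how much drug was taken or how well instructions were followed. This is the only efficacy sensitivity population in the SAP. SAP 10.4 imputes nothing and only lists Early Termination data from before Day 170, so no other planned efficacy sensitivity analysis deals with incomplete treatment. If the set does not hold the subjects its name suggests, agreement or disagreement with the ITT result is hard to read.

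**Working it through.** The plan gives no worked compliance value to reproduce, so the formula in SAP 15.2 is applied as written.

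**Inputs.** Planned course 182 days (Protocol 7.2); 2 capsules a day (Protocol 6.3, SAP 15.2), so 364 planned capsules; gate 80% to 120% (SAP 8); Paxlovid hold 12 days (Protocol 9.3.1). Hold lengths other than 12 days are assumptions, because the documents give none.

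**Formula.** Compliance = 100 × capsules taken / [2 × (last dose day − first dose day + 1)].

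**1. Dosing stops and does not resume, with no doses missed before that.**
- Last dose Day 98: 196/196 = 100%. Against the planned course, 196/364 = 53.8%.
- The result is 100% wherever dosing stops. At Days 28, 56, 91 and 126 the share of the planned course is 15.4%, 30.8%, 50.0% and 69.2%.
- If the Day 98 subject also takes the single Day 182 clinic dose: 198/364 = 54.4%. One more day of drug moves the subject from inside the set to outside it.

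**2. An ordered hold of h days, then dosing resumes to Day 182, with every permitted dose taken.** Compliance = (182 − h)/182.

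| Hold (days) | Compliance | In the set, if completed? |
|---|---|---|
| 12 | 170/182 = 93.4% | Yes |
| 24 | 158/182 = 86.8% | Yes |
| 36 | 146/182 = 80.2% | Yes |
| 37 | 145/182 = 79.7% | No |
| 48 | 134/182 = 73.6% | No |

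A hold on its own therefore excludes from 37 days. A shorter hold can matter in combination: a 12-day hold plus 25 other missed days gives 145/182 = 79.7% (out), although 145/170 = 85.3% of permitted doses were taken.

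**3. The same subjects with a planned-course denominator.**
- *Exposure* (hold days kept in): the Day 98 subject scores 53.8% and is out. The 37-day hold scores 79.7% and is also out. With no missed doses, the last dose must fall on Day 146 or later (146/182 = 80.2%; 145/182 = 79.7%).
- *Adherence to instructions* (ordered hold days subtracted): the 12-day hold scores 170/170 = 100% and the 37-day hold 145/145 = 100%; both are in. An ordered hold that begins after Day 98 and is never lifted lasts 182 − 98 = 84 days and also scores 98/98 = 100%. Under this option, the definition of completion decides that subject's membership.

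No single denominator both screens out short exposure and forgives ordered holds.

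**The case against.** The strongest reply is that the protocol's own procedures catch most half-treated subjects.

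- SAP 8 also requires completion. Protocol 8.4 says subjects should be withdrawn for conditions that necessitate termination, naming the events in 6.3.1. Protocol 8.5.1 and 9.2.11 bring those who discontinue prematurely to an Early Termination visit within 2 weeks of the last dose. A Day 98 stop handled that way ends by about Day 112, and the subject is outside the set.
- Drug is given in clinic on Days 28, 56, 98, 154 and 182 (Schedule of Assessments). A subject who stops at home after Day 98 but takes the Day 154 and Day 182 clinic doses scores 200/364 = 54.9% and is correctly excluded.
- No section describes scheduled off-drug follow-up to Day 182.
- SAP 15.2 also summarizes doses taken, total dose, duration and interruptions by treatment, so short exposure would be visible. First-to-last-dose compliance is a sound descriptive measure of behavior while on drug.

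All of this stands, and it narrows the first case sharply. It does not close it. The temporary stop in Protocol 6.3.1 has no stated limit, SAP 9.1 counts stopping treatment and stopping the study separately, and SAP 8 defines completion only as not withdrawing early. A subject whose hold is never lifted can therefore be recorded as completing.

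A reader might infer that subjects treated for half the trial will readily enter the set, or that Paxlovid users will be thrown out. The documents support neither: the first needs the narrow route above, and even three 12-day holds (36 days) still pass at 80.2%.

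**Conclusion.** The mismatch is real and visible in the SAP text. The gate in section 8 refers to the whole study, while the formula in 15.2 ends at the last dose taken and makes no allowance for ordered holds. For an individual subject the error can be large (100% against 54%), but how many subjects it would affect is unknown, because the documents give no hold durations or frequencies. Exclusion by a hold alone needs 37 days or more, an assumed length that no section states.

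It is tempting to go further and say that the misclassification would fall mainly on the CT1812 arms and distort the comparison with placebo. Protocol 3.3 makes that plausible but does not establish it. It reports liver enzyme rises on CT1812, but the four increases in the multiple-dose study include one on placebo, the episodes in the ongoing Alzheimer's study are not attributed to arm, and there are no rates for long or unresumed holds. Direction and size cannot be stated.

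The key MoCA comparison uses the ITT population and is unaffected. The consequence is confined to the completers/compliers sensitivity analyses and to the compliance table in SAP 15.2, which uses the same formula. No clinical hold or restart rule is in question.

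**What to change.** Before unblinding, amend SAP 8 and 15.2 as follows.

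1. For membership, run the denominator from first dose to the Day 182 visit date, at two capsules a day, rather than to the last dose taken.
2. State one purpose for the set. If it is adequate exposure, keep ordered hold days in the denominator and accept that long holds exclude. If it is adherence to instructions, subtract documented protocol-ordered hold days.
3. Report the other figure descriptively. The present first-to-last-dose percentage can stay as a descriptive row labeled as compliance while dosing.
4. State whether a subject off drug at Day 182 counts as having completed the study. Under the adherence option this settles the never-resumed hold.
5. Align the boundary: section 8 appears to admit exactly 80%, while the table in 15.2 puts it in the lowest category.

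The cost is wording and minor programming. The interruption summary already planned in 15.2 should draw on the same hold records. SAP 16 lists the set as an SAP addition not defined in the protocol, so no protocol amendment appears necessary. The downside is a possibly slightly different set size.

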### 15.3 Clinical Laboratory Evaluation

Laboratory parameters (serum chemistry, hematology, coagulation, and continuous urinalysis parameters) will be summarized using descriptive statistics at baseline and at each post baseline time point. Changes from baseline will also be summarized.

In addition, shift tables relative to the laboratory normal range (i.e., low-normal-high at baseline versus low-normal-high at post baseline) will be provided to assess changes in serum chemistry and hematology laboratory values from baseline to each post baseline time point.

Subjects with elevated ALT, AST, ALT or AST  $\geq 3 \times$  ULN, ALT, AST, ALT or AST  $\geq 5 \times$  ULN, ALT, AST, ALT or AST  $\geq 10 \times$  ULN, and ALT, AST, ALT or AST  $\geq 20 \times$  ULN will be summarized. Categories will be cumulative, i.e. a subject with an elevation of AST  $\geq 5 \times$  ULN will also appear in the categories  $\geq 3 \times$  ULN.

Separate listings for chemistry, hematology, coagulation, liver function, and urinalysis results will be presented.

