3.2 Nonclinical Experience

3.2.1 Nonclinical Pharmacology Studies

CT1812 is a lipophilic isoindoline formulated as a fumarate salt and is the result of a structure-based medicinal chemistry optimization program comprised of over 300 analogs. CT1812's properties are fully described along with all preclinical studies in the Investigator Brochure. CT1812 has a high affinity at the target receptor sigma-2/PGRMC1 (S2) and is >100-fold selective for this receptor over other receptors and ion channels. Dose-limiting toxicities at higher doses in both species appear to be hypercalcemia and renal tubular damage, both of which are non-invasively monitored via measurement of serum calcium and urinary markers of renal tubular injury such as kidney injury molecule 1 (KIM-149,50).

In vitro pharmacodynamic (PD) studies confirmed CT1812 target binding specificity, affinity and engagement, including the prevention and reversal of A β oligomer binding and the prevention of A β oligomer-induced synapse loss.

In vivo PD studies confirmed the desired consequences of target engagement, including cognitive improvements in an aged transgenic mouse model of AD following oral administration of an apparently tolerated dose of CT1812 daily for 9 weeks. Additional *in vivo* PD studies, using an A β oligomer detecting microelectrode in an aged transgenic mouse model of AD, demonstrated that administration of CT1812 caused an acute increase in soluble A β oligomers in the interstitial fluid of the hippocampus and a sustained increase in soluble A β oligomers in the CSF of the lateral ventricle of the brain. These increases in soluble A β oligomers occurred without a change in the amount of soluble A β 1-40, indicating that displacement of A β oligomers occurred following treatment with CT1812.

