3.2.3 Nonclinical Safety Studies

Two hERG (human Ether-à-go-go Related Gene) assays were performed to assess effects of CT1812 on the rapidly activating delayed rectifier potassium channels (IKr) using channels stably transfected and over-expressed in Chinese Hamster Ovary cells. Using whole-cell patch clamp electrophysiology, CT1812 was tested in both studies in duplicate at concentrations of 1, 3, 10, and 30 mM. Mean IC_{50} values of 26 mM and 0.6 mM were determined in the first and second assay, respectively. Reasons for the differing results are unknown. However, no ECG effects were noted in the telemeterized dog cardiovascular safety study or in the multiple-dose dog pivotal toxicology study when tested up to high-dose mean C_{max} values of approximately 4 μM .

Safety pharmacology studies with rats revealed no apparent effects on CNS or pulmonary parameters following single oral dosages that exceeded the maximum tolerated dose in this species.

General toxicology studies with rats and dogs following oral dosing of CT1812 revealed dose-limiting toxicity that manifested as degenerative changes in the proximal tubules of kidney, hypercalcemia, and vascular mineralization and/or degeneration involving multiple tissues and organs in each species. Tolerable and intolerable dosages and exposures, characterized with each species, informed the selection of dosages for this trial.

Additionally, toxicology studies revealed several test article-related clinical laboratory changes, including elevated serum creatinine and/or BUN that correlated with mild weight loss, elevated serum calcium and reduced urinary specific gravity. The exact mechanism for these changes cannot be determined from those studies. Serum and urine tests will be performed in this trial to evaluate the effect of study drug administration on renal function (including serum creatinine, serum calcium, urine calcium).

Genetic toxicology studies revealed no positive responses in bacterial and mammalian in vitro assays, or in an in vivo mouse bone marrow micronucleus assay when tested up to maximally feasible dosages.

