12.1.4 Clinical Laboratory Tests

Hematology testing will include red blood cell count, erythrocyte mean corpuscular hemoglobin concentration (MCHC), erythrocyte mean corpuscular volume (MCV), hematocrit, hemoglobin, leukocyte count, and absolute counts of monocytes, neutrophils, basophils, eosinophils and platelets. Coagulation testing (prothrombin time [PT/INR]) will be performed at screening and Day 154 only.

Serum chemistry analyses will include glucose, calcium, albumin, total protein, sodium, potassium, bicarbonate, chloride, magnesium, blood urea nitrogen (BUN), creatinine, creatine kinase, alkaline phosphatase, ALT, AST, bilirubin, lipase, lactate dehydrogenase (LDH) and phosphorus.

In instances where either the AST or ALT are 2x the ULN these tests will be repeated and documented as an unscheduled visit.

Blood draws should occur within 1 hour of urine collection.

Urinalysis will include osmolality, creatinine, calcium, sodium, turbidity, color, specific gravity, pH, protein, glucose, ketones, bilirubin, blood, urobilinogen, nitrite, leukocytes, and microscopic particles. Urine should not be first morning void. Microscopic examination will be performed if urinalysis results are abnormal for bacteria, casts, epithelial cells, erythrocytes, or leukocytes. Urine should be collected within one hour of blood draws for hematology and chemistry panels. It should not be first morning void. Trace protein will be considered positive.

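### Urine calcium, a named renal safety test, is summarized only as measured in a spot sample, so dilution of the urine by the drug, if it occurs, could hide a rise in calcium excretion

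*SAP*

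**What the plan says.** Protocol 3.2.1 states the animal background: "Dose-limiting toxicities at higher doses in both species appear to be hypercalcemia and renal tubular damage". Protocol 3.2.3 adds that "toxicology studies revealed several test article-related clinical laboratory changes", and these include "elevated serum calcium and reduced urinary specific gravity". It then says that serum and urine tests will be done to "evaluate the effect of study drug administration on renal function (including serum creatinine, serum calcium, urine calcium").

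Protocol 12.1.4 sets out the urine panel: "Urinalysis will include osmolality, creatinine, calcium, sodium, turbidity, color, specific gravity, pH, protein" and further analytes. The sample must not be the first void of the morning, and blood is drawn within an hour of it. The schedule of assessments (Table 1) has chemistry, hematology and urinalysis at every visit and shows no timed or 24-hour collection.

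SAP 15.3 covers the analysis: "Laboratory parameters (serum chemistry, hematology, coagulation, and continuous urinalysis parameters) will be summarized using descriptive statistics" at baseline and at each later time point, together with changes from baseline. Shift tables are planned for serum chemistry and hematology only. Urinalysis results are also listed. The derived variables under Standard Calculations in SAP Appendix A are durations, unit conversions, BMI, change and percent change. None of them is a urine index.

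**The concern.** The protocol gives a reason to measure urine calcium and, in the same paragraph, describes an animal effect that could disturb the measurement. Concentration in a spot sample falls when urine is more dilute, even if the amount of calcium excreted is unchanged. If the active arms became more dilute than placebo, their calcium concentrations would be lower for that reason alone. Randomization would not balance this, because the dilution would itself be a treatment effect.

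Safety is the primary objective. At stake is whether the urine calcium rows of the safety tables can show a rise in calcium excretion if one occurs. Creatinine, osmolality and specific gravity are measured in the same urine, so the data needed for a correction will exist, but the SAP does not combine them.

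**Working it through.** The documents give no figure for urine calcium, so there is no stated result to reproduce. The check is arithmetic on the planned summary, with assumed sizes shown as a range.

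**Inputs from the documents.** Urine calcium is a named renal test and lower specific gravity is an animal finding (Protocol 3.2.3). Calcium and creatinine are measured in one spot urine (Protocol 12.1.4). The value is summarized as measured (SAP 15.3). The planned size is 40 per arm (SAP 5). No reporting unit is given. That the summary is of a concentration is inferred from a spot sample with no derived urine variable.

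**Inputs assumed.** Dilution of 20% to 40%, rises in calcium excretion, and the log-scale SDs used below. None of these has a source in the documents.

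**Step 1: what the planned row shows.** Concentration is excretion divided by urine flow. Let E be the ratio of calcium excretion to its baseline and F the ratio of urine flow to its baseline. The observed concentration ratio is E/F. With E = 1 + rise and 1/F = 1 − dilution, this is (1 + rise) × (1 − dilution).

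**Step 2: the rise that tabulates as no change.** Set the product to 1, so rise = 1/(1 − dilution) − 1.

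- Dilution 20%: 1/0.80 − 1 = 0.25, a rise of 25%.
- Dilution 30%: 1/0.70 − 1 = 0.43, a rise of 43%.
- Dilution 40%: 1/0.60 − 1 = 0.67, a rise of 67%.

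**Step 3: a partly hidden rise.** Take E = 1.5 as an assumed case.

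| Urine flow F | Change in concentration (E/F − 1) | Change in calcium/creatinine |
|---|---|---|
| ×1.0 | +50% | +50% |
| ×1.25 | +20% | +50% |
| ×1.5 | 0% | +50% |

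**Step 4: why the ratio helps, and its limit.** Let C be the ratio of creatinine excretion to its baseline. The calcium/creatinine ratio changes by (E/F)/(C/F) = E/C, so flow cancels. It shows E exactly only if C = 1. If creatinine excretion fell by 20%, the ratio would rise by 1/0.80 − 1 = 25% with no change in calcium excretion.

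**Step 5: noise when the drug has no effect on dilution.** Suppose the log-SD of the calcium/creatinine ratio is 0.4 to 0.6 and hydration adds an independent log-SD of 0.4 to 0.6. The log-SD of the concentration is then between √(0.4² + 0.4²) = 0.57 and √(0.6² + 0.6²) = 0.85. For E = 1.5 (log 0.405), 40 versus 40 and two-sided 0.05, power would be 0.57 to 0.89 for the concentration and 0.86 to 0.99 for the ratio. At F = 1.25 the figure for the concentration drops to 0.16 to 0.30. SAP 15.3 plans no test, so these values only illustrate precision.

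**The case against.** The strongest reply is that the masking scenario joins two things that the documents do not show together. Protocol 3.2.3 reports raised serum calcium and lower specific gravity in animals. It does not report raised urinary calcium excretion, gives no size for the dilution, and says the mechanism could not be determined. Protocol 3.2.1 places the dose-limiting toxicities at higher doses. Protocol 3.3 reports no evidence of renal toxicity in the Phase 1 healthy-volunteer trial on serum creatinine, BUN or cystatin C, with multiple dosing at 280 to 840 mg for 14 days. All of this stands, which is why the point is conditional. The Phase 1 statement does not mention urine calcium, however, and this trial doses for 182 days.

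A second reply is that dilution would be visible. Osmolality, specific gravity and urine creatinine are summarized in their own rows, and flat calcium beside falling creatinine would be a clue. That is fair, but separate group rows do not give a per-subject ratio, and the listings leave the calculation to the reader.

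Third, creatinine is an imperfect denominator here. Protocol 3.2.3 links the creatinine and BUN changes in animals to mild weight loss. If weight or muscle mass changes on drug, creatinine excretion may change too and would not cancel within a subject. This stands and shapes the fix.

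Finally, SAP Appendix B refers to separate dataset specifications, and the table index in Appendix C is not in the text available. A ratio could be defined there, but the SAP's own analysis and formula sections do not define one.

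**Conclusion.** The point holds as a low-cost improvement to a descriptive safety summary. As planned, the urine calcium rows cannot separate a change in calcium excretion from a change in urine dilution. For assumed dilution of 20% to 40%, a true rise of 25% to 67% could tabulate as no change. The arithmetic is exact; the sizes are assumptions. Whether any dilution occurs in humans at the trial doses is not known.

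Several stronger conclusions might be inferred, and the documents do not support them:

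- That the comparison between arms is confounded. It could be, but neither dilution nor raised calcium excretion is shown in humans.
- That the table will point the wrong way. This needs flow to rise more than excretion (excretion ×1.5 with flow ×2.0 gives 1.5/2.0 − 1 = −25%), and nothing in the documents indicates that.
- That urine calcium is the only urine signal. The list in Protocol 3.2.3 is given as examples, and Protocol 12.1.4 includes other urine tests, such as protein, glucose and blood.
- That hypercalcemia or falling renal function would be missed. Serum calcium and serum creatinine keep their summaries and shift tables.
- That fractional excretion of sodium is needed. No section names a sodium signal; it is optional.

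**What to change.** In SAP 15.3, keep the raw urine calcium and add the per-subject urine calcium/creatinine ratio from the same sample. Summarize it by arm and visit with change from baseline. Use medians and quartiles, or the log scale, because such ratios are usually skewed. Add calcium adjusted for urine osmolality as a check, since it does not depend on creatinine excretion, and read the ratio beside the weight summaries in SAP 15.4. Put both formulas under Standard Calculations in SAP Appendix A.

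The cost is two derived variables and their table rows. The analytes are already in the urine panel at every visit, so no new sample, visit or protocol change is needed. The addition should be made before unblinding, because SAP 6 labels anything added later as post hoc. The downside is that the creatinine ratio can move if weight or muscle mass changes on drug, which is the reason for the osmolality check.

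### SAP 15.3 plans no table of graded urine protein and no count of subjects whose creatinine rises from their own baseline, although renal tubular damage is a named dose-limiting animal toxicity

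*SAP*

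**What the plan says.** **Why the kidney matters here.** Protocol 3.2.1: "Dose-limiting toxicities at higher doses in both species appear to be hypercalcemia and renal tubular damage". Protocol 3.2.3 describes "dose-limiting toxicity that manifested as degenerative changes in the proximal tubules of kidney, hypercalcemia, and vascular mineralization", and reports raised serum creatinine and/or BUN in the animal studies. It then commits the trial: "Serum and urine tests will be performed in this trial to evaluate the effect of study drug administration on renal function". Assessing safety and tolerability is the primary objective (Protocol 4.1, SAP 3.1).

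**What is collected.** Chemistry, hematology and urinalysis are taken at every visit (Protocol Table 1). Protocol 12.1.4: "Urinalysis will include osmolality, creatinine, calcium, sodium, turbidity, color, specific gravity, pH, protein, glucose, ketones, bilirubin, blood", among others. The same section adds: "Trace protein will be considered positive". That implies protein is reported as a grade rather than as a measured quantity.

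**What SAP 15.3 tabulates.**
- "Laboratory parameters (serum chemistry, hematology, coagulation, and continuous urinalysis parameters) will be summarized using descriptive statistics", at baseline and each later time point. "Changes from baseline will also be summarized".
- "shift tables relative to the laboratory normal range", in low/normal/high categories, for serum chemistry and hematology, at each post-baseline time point.
- Cumulative multiple-of-ULN counts, for ALT and AST only.
- Listings, including urinalysis.

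SAP 6 defines the continuous summary as n, mean, SD, median, minimum and maximum.

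**The concern.** The SAP already counts subjects in two other places: ALT/AST by multiples of ULN (15.3), and QTcF by change of more than 30 or 60 ms from the subject's own baseline (15.6). The kidney is a dose-limiting target organ in animals and has no such count.

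Two gaps follow. Urine protein, if graded, is not a continuous parameter and urinalysis has no shift table, so 15.3 gives it no comparison between arms. For creatinine, a normal-range shift is insensitive to a rise that starts low in the range, and a mean or maximum change does not say how many subjects rose. At stake is whether a reader of the laboratory tables can compare arms on the number of subjects with a renal change, over 182 days of dosing at ages 50 to 85.

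**Working it through.** The documents state no figure on this point, so there is none to reproduce.

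**Step 1: when a shift table misses a 50% rise.** Let B be baseline creatinine and U the upper limit of normal. If B is within range, 1.5 × B stays within range when B ≤ U/1.5. For U = 1.2 mg/dL that is B ≤ 0.80; for U = 1.3, B ≤ 0.87; for U = 1.0, B ≤ 0.67.

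**Step 2: how often that happens.** The documents give neither a creatinine distribution nor a ULN, so these are assumptions. Baseline is taken as normal with mean m and SD s, nobody is below 0.5 mg/dL, and a 50% rise is taken as equally likely at any baseline. Among in-range baselines:

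share hidden = [Φ((U/1.5 − m)/s) − Φ((0.5 − m)/s)] / [Φ((U − m)/s) − Φ((0.5 − m)/s)]

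- Central case, m = 0.9, s = 0.2, U = 1.2: (0.3085 − 0.0228)/(0.9332 − 0.0228) = 0.2857/0.9104 = **31%**.
- Lowest, m = 1.0, s = 0.15, U = 1.0: (0.0131 − 0.0004)/(0.5000 − 0.0004) = **about 3%**.
- Highest, m = 0.8, s = 0.15, U = 1.3: (0.6716 − 0.0228)/(0.9996 − 0.0228) = **66%**.

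The range for m 0.8-1.0, s 0.15-0.20, U 1.0-1.3 is therefore about 3% to 66%. It is wide because U/1.5 moves across the middle of the assumed distribution.

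**Step 3: what the change-from-baseline table adds.** With 40 subjects per arm, four subjects each rising 0.45 mg/dL (50% of 0.9) move the arm mean by 4 × 0.45/40 = 0.045 mg/dL. The maximum shows the largest of the four rises at that visit. No planned statistic shows that there were four.

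**Step 4: urine protein.** 15.3 restricts descriptive urinalysis tables to continuous parameters, restricts shifts to chemistry and hematology, and sends urinalysis results to a listing. None of the stated tables takes a graded result.

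**Step 5: which visits count.** SAP 10.4 says summary tables use nominal visits, and early-termination data before Day 170 are listed only. The rule sits in the efficacy chapter, but it is worded for summary tables generally and 15.3 states no visit rule of its own. If it is applied to laboratory data, the termination value of a subject who stops early enters no laboratory table.

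**The case against.** Several points on the other side stand, and they limit the concern.

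- **Creatinine is not confined to shifts.** Descriptive statistics and change from baseline are planned, with minimum and maximum. A reader might infer that marked rises would leave the tables showing no renal signal. The documents do not support that: one subject in 40 doubling from 1.0 would appear as a maximum change of about +1.0 mg/dL. What is missing is the count.
- **Hypercalcemia is already visible.** A move from normal to high calcium appears in the chemistry shift table at each visit.
- **Baselines above range should be uncommon.** Because eGFR down to 50 mL/min is eligible, a reader might infer a sizeable group that starts high and stays high. Protocol 9.2.1, however, excludes subjects whose abnormal screening result persists on repeat. The working above therefore uses in-range baselines only.
- **The analytes that Protocol 3.2.3 lists by name are tabulated.** Serum creatinine, serum calcium and urine calcium all receive summaries with change from baseline. Urine protein is not named there.
- **The liver emphasis has a reason.** Protocol 3.3 reports liver enzyme elevations in humans, and no evidence of renal toxicity in the healthy-volunteer study. Multiple dosing there lasted 14 days, however, so it does not settle a 182-day question.
- **Other routes exist.** A laboratory abnormality judged clinically significant is an adverse event (Protocol 12.2.1) and reaches the TEAE tables. The DSMB and medical monitor also review safety data. The adverse-event route depends on investigator judgement and is not a systematic count.
- **Absence cannot be proved completely.** The itemised list of tables under SAP Appendix C is not in the text available, and SAP 6 has a general rule for categorical variables. That rule says how to summarise a categorical variable; 15.3 decides which urinalysis parameters are summarised.

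**Conclusion.** The point holds as a cheap improvement. SAP 15.3 states no table of graded urine protein and no count of subjects with a defined creatinine rise from their own baseline, while renal tubular damage is one of the named dose-limiting animal toxicities. The planned creatinine tables show the largest value but not the number of subjects affected.

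The size is uncertain. The 31% central figure and the 3% to 66% range rest wholly on an assumed creatinine distribution, an assumed ULN, and rises being unrelated to baseline. It cannot be claimed from the documents that most, or even many, 50% rises would be hidden. The urine protein gap rests on protein being reported as a grade, which Protocol 12.1.4 implies but does not state. The loss of early-termination values is conditional on SAP 10.4 being applied to laboratory tables.

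**What to change.** Add to SAP 15.3, by arm, using each subject's worst post-baseline value at any scheduled, unscheduled or early-termination visit:

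1. Number and percent of subjects with serum creatinine at least 1.5 times, and at least 2 times, their own baseline.
2. A baseline-to-worst shift for urine protein, negative versus positive, with trace counted as positive as in Protocol 12.1.4.

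A worst-value count of calcium above the normal range is optional, since the shift table already shows it by visit. State in 15.3 whether the Day 170 rule of SAP 10.4 applies to laboratory summaries. These are reporting categories only and imply no rule for managing subjects.

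Cost: a short SAP addition and about two extra tables from data already collected.
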